**Investigational Agent:**

Drug Name:	Prednisone (under multiple trade names)
IND Number:	N/A (exempt)
Sponsor:	N/A
Drug Supplied By:	NIH Pharmacy

## **STATEMENT OF COMPLIANCE**

The trial will be carried out in accordance with International Council for Harmonisation Good Clinical Practice (ICH GCP) and the United States (US) Code of Federal Regulations (CFR) applicable to clinical studies (45 CFR Part 46, 21 CFR Part 50, 21 CFR Part 56, 21 CFR Part 312, and/or 21 CFR Part 812)

National Institutes of Health (NIH)-funded investigators and clinical trial site staff who are responsible for the conduct, management, or oversight of NIH-funded clinical trials have completed Human Subjects Protection and ICH GCP Training.

The protocol, informed consent form(s), recruitment materials, and all participant materials will be submitted to the Institutional Review Board (IRB) for review and approval. Approval of both the protocol and the consent form must be obtained before any participant is enrolled. Any amendment to the protocol will require review and approval by the IRB before the changes are implemented to the study. In addition, all changes to the consent form will be IRB-approved; a determination will be made regarding whether a new consent needs to be obtained from participants who provided consent, using a previously approved consent form.

## List of Abbreviations

ACR	American College of Rheumatology
AE	Adverse Event/Adverse Experience
AEC	Absolute Eosinophil Count
AF	Activation Function (AF-1, AF-2)
CBC	Complete Blood Count
COPD	Chronic Obstructive Pulmonary Disease
CRF	Case Report Form
CRIMSON	Clinical Research Information Management System of the NIAID
ERR	Eosinophil Response Rate
EGID	Eosinophilic Gastrointestinal Disease
FIP1L1	FIP1-like1
F/P	FIP1L1-PDGFR $\alpha$
GC	Glucocorticoid
GR	Glucocorticoid Receptor
GRE	Glucocorticoid Response Element
HES	Hypereosinophilic Syndrome
IL	Interleukin
IRB	Institutional Review Board
LFT	Liver function test
N	Number (typically refers to the number subjects or the sample size)
OHSR	Office of Human Subjects Research
OCRPRO	Office of Clinical Research Policy and Regulatory Operations
PBMC	Peripheral Blood Mononuclear Cells
PDGFR	Platelet-derived growth factor
PHI	Protected Health Information
PI	Principal Investigator
RNA PAX	Ribonuclease PAXgene blood tube
SAE	Serious Adverse Event/Serious Adverse Experience

## Protocol Summary

Full Title:	Assessment of Glucocorticoid Responsiveness and Mechanisms of Resistance in Hypereosinophilic Syndromes
Short Title:	Glucocorticoid responsiveness in HES
Principal Investigator:	[name]
Sample Size:	N=40
Accrual Ceiling:	40
Study Population:	100 children and adults, ages 7-100
Accrual Period:	6-13 years
Study Design:	Single blinded clinical trial
Study Duration:	14 years
Start Date:	Oct 2011
End Date:	Dec 2026
Primary Objective:	To develop a model to determine whether a single dose glucocorticoid (GC) challenge can be used to predict GC responsiveness in subjects with HES
Secondary Objectives:	To delineate the mechanisms of decreased GC responsiveness in GC-resistant subjects.
Exploratory Objectives:	To assess in-vitro correlates of therapeutic responsiveness in HES.
Endpoints:	Primary: GC responsiveness, defined as the lowest dose of prednisone at which eosinophils remain <1000/ $\mu$ L, for at least two consecutive weekly blood draws, and at which symptoms are controlled as determined by the investigator Secondary: Identification of GC non-responders and/or suboptimal responders for studies of GC resistance in HES. Exploratory: Delineation of the mechanisms of GC resistance and in-vitro correlates of response in subjects with HES.

## Précis

This study aims to develop a model to determine whether a single, oral, weight-based dose of glucocorticoid (GC) can predict clinical and biologic response to GC's over the long term in subjects with hypereosinophilic syndrome (HES). Subjects with FIP1L1/PDGFR $\alpha$ -negative HES, who are symptomatic with eosinophil count  $>1500/\mu\text{L}$  and receiving  $\leq 10$  mg prednisone daily, will be enrolled. A single oral dose of prednisone (1 mg/kg rounded to the nearest 5mg) will be administered. Eosinophil count and various laboratory parameters will be assessed at 2 hours, 4 hours and 24 hours following prednisone administration (investigators will be blinded to the results of the eosinophil counts). The subjects will then begin GC therapy at 30 mg prednisone daily followed by a standardized taper. The lowest dose of GC at which symptoms and eosinophilia are controlled will be compared to the change in eosinophil count at 2, 4 and 24 hours post-challenge. Mechanisms and in vitro correlates of GC resistance will also be explored.

# 1. Introduction & Background

## 1.1. Rationale

Although glucocorticoids (GC) are the mainstay of therapy for many autoimmune and inflammatory conditions, not all patients respond equally, and high doses of inhaled or systemic GCs are often used in non-responders. Consequently, GC resistance is an active area of study in asthma, smokers with asthma, chronic obstructive pulmonary disease (COPD), and other inflammatory disorders. GCs are considered standard first-line therapy in patients with hypereosinophilic syndrome (HES) who lack the FIP1L1-PDGFR $\alpha$  (F/P) mutation. In fact, more than 85% of patients with HES studied retrospectively had a complete or partial response to GC at 1 month(1). Although decreased expression of the GC receptor on the surface of eosinophils was implicated in 3 out of 5 patients with GC-resistant HES(2), the mechanisms of decreased or absent GC response in diverse variants of patients with HES are largely unexplored.

A single-dose prednisone challenge has been proposed as a way to assess steroid-responsiveness and measure prognosis in patients with F/P negative HES. Although patients presenting with HES are typically treated with a large dose of GC followed by a steroid taper, the utility of this approach has not been validated. Studying the effects of a steroid challenge would be beneficial for 4 reasons. First, an eosinopenic response after a 1 mg/kg dose could provide information about the efficacy of high dose GC in the event of rapidly progressive disease. Second, if the acute response to a single dose GC challenge were able to predict the maintenance dose after a taper, this might allow patients to spend less time on higher doses. Third, the lack of response to a steroid challenge would identify patients for whom a trial of steroids would be unwarranted allowing faster institution of alternate therapies for HES. Finally, as subjects with GC-resistant HES are systematically identified in a standardized fashion, further mechanistic work into causes of resistance, included elucidation of signaling pathways, glucocorticoid receptor function, and perhaps even genetic reasons for resistance may be explored.

## 1.2. Background

Glucocorticoids act on a number of glucocorticoid-responsive genes relevant to inflammatory conditions via the glucocorticoid receptor (GR). The GR itself is composed of a DNA ligand and an immunogenic or N-terminal domain. Alternative splicing of the GR gene generates 2 receptor isoforms. The classically active form is GR $\alpha$ , which resides in the cytoplasm and is expressed in cells of most organs and tissues in the human body. GR $\beta$ , the second isoform, acts as a dominant negative receptor. Administration of GCs in the setting of inflammatory and allergic conditions results in expression of anti-inflammatory cytokines, as well as diminished expression of inflammatory or adhesion molecules on airway or vascular epithelium. A number of mechanisms have been proposed to explain decreased GC responsiveness. The following section describes some of these mechanisms and their potential relevance in HES (Appendix G, Figure 1) .

### 1.2.1. Inappropriate Absorption of Glucocorticoids

While there have been no studies of GC absorption in HES, it is possible that patients with eosinophilic involvement of the GI tract might have difficulty with GC absorption (Appendix G, Figure 1). Although GCs are used for the treatment for eosinophilic gastrointestinal disease (EGID), especially in the setting of malabsorption, the mechanism of GI involvement in HES may be different (mucosal edema instead of eosinophilic inflammation, for example). Furthermore, it is not clear that oral dosing in the form of prednisone has similar bioavailability or pharmacokinetics of absorption to the compounded liquid forms of GC used most often in EGID.

### 1.2.2. Alterations in Glucocorticoid Receptor function

GR function involves multiple steps, including 1) binding of GC to the receptor, 2) translocation of the GC-receptor complex into the nucleus, and 3) direct and indirect effects on GR response elements leading to modulation of the cytokine response (Appendix G, Figure 1). Abnormalities in any of these could potentially lead to decreased GC responsiveness.

Increased expression of GR $\beta$  in place of the active GR $\alpha$  has been reported in steroid insensitive nasal polyps(3), fatal asthma(4), steroid resistant asthma(5), and other steroid insensitive inflammatory diseases(6); however, the degree to which differential expression of GR isoforms contributes to steroid resistance remains controversial. To complicate matters further, an additional cohort of receptor proteins produced by alternative translation initiation from a single GR mRNA species was recently described and results in an increased number of GR isoforms(7). GR isoform expression has not been evaluated in HES to date.

One of the ways that glucocorticoids exert their anti-inflammatory effects is through inhibition of transcription factors, which in turn alter cytokine expression profiles. Differential expression of the NF $\kappa$ B DNA binding unit (NFKB1), STAT-4 and IL-4R in stimulated PBMCs predicted the GC resistant phenotype in asthmatics(8) Furthermore, cytokine footprints of decreased GC responsiveness have been described in patients with eosinophilic esophagitis and asthma. In one study of patients with eosinophilic esophagitis, non-responders to budesonide therapy had elevated numbers of TGF $\beta$ 1 positive cells compared with responders(9). Studies in asthmatic patients have demonstrated increased number of cells expressing Th2 cytokines, including IL-4(5, 10), IL-5(5), and IL-13(10), as well as increased IFN $\gamma$ (5) mRNA in bronchoalveolar lavage (11) from GC resistant subjects. The cytokine phenotype of GC resistance in HES has not been studied.

Despite the complexity of GC signaling (Appendix G, Figure 2)(12), some progress has been made in evaluating kinetic phosphorylation events occurring at the N-terminus phosphorylation sites of the GR after binding of corticosteroids. Phosphorylation events affect subcellular transport of the GR and therefore have effects on GR function in the setting of inflammatory conditions. Examples of assessment of phosphorylation events in asthma include: demonstration of elevated p38 MAPK and pERK1/2 in asthma

patients compared to controls(11), and elevated p38 MAPK reduction of nuclear GR-ligand binding affinity in steroid-dependent asthmatics compared with controls(13). It has also been proposed that phosphorylation of the GR might affect ligand affinity suggesting a role for tissue or cell specific responses.

### **1.2.3. Glucocorticoid effects on trafficking and eosinophil transcriptomics**

At the time of initiation of this study, early (<4h) kinetics of glucocorticoid action on eosinophils were not well described. Samples from this and other studies were subjected to transcriptomic evaluation to determine early kinetics of eosinophil decline. More recent knowledge suggests that there is a substantial decline of eosinophils in the peripheral circulation (at least in normally responsive eosinophils) by 3 hours. More striking, the major genes of interest in apoptosis and trafficking were noted to be up or down-regulated by 2 hours after GC administration. Of the 414 genes differentially expressed in eosinophils in the first 2 hours after prednisone administration, 12 are known to be involved in leukocyte migration: *CXCR4*, *RIPOR2*, *PREX1*, *CCR1*, *PTGER4*, *SWAP70*, *IL16*, *PIK3CG*, *NLRP12*, *CD244*, *S1PR1*, and *CSF1*. Four of these genes were significantly differentially expressed prior to the initial decline in circulating eosinophils, which occurred in the interval between 60 and 120 minutes. In vitro and flow cytometric studies demonstrated that *CXCR4* is upregulated in response to steroids and we hypothesize this might be important in trafficking of eosinophils from the peripheral blood into tissues (14). For this reason, we are splitting amount of research blood drawn in the 4 hour timepoint into a 2 and 4 hour timepoint in order to be able to study the exploratory endpoints without losing valuable data at the 4 hour timepoint. The primary clinical endpoint at 4 hours remains unchanged as it is not appropriate or possible to change the primary endpoint at this juncture.

Ultimately, understanding the various processes that predict decreased GC responsiveness would assist in numerous ways in the care of patients with HES. First, it would allow tailoring of treatment regimens for patients with HES. Second, development of assays or biomarkers that can predict decreased responsiveness could reduce GC use in such patients by preventing unnecessary treatment trials in patients unlikely to respond and accelerating the time to maintenance dosing. Thirdly, understanding the underlying mechanisms of GC resistance might pave the way for more effective anti-inflammatory treatments or adjuncts to GC, as has been demonstrated in COPD, where theophylline and selective PI3K $\delta$  inhibitors have a synergistic effect with GC administration (15). Better understanding of transcriptional changes in eosinophils might provide additional insight into receptor ligands on eosinophils, their role in trafficking, and might pave the way for further research into therapeutic implications of these findings. Finally, insights into the causes of decreased responsiveness of eosinophils to GC and in HES may have implications for other inflammatory and allergic disorders.

## **2. Study Objectives**

### **2.1. Primary Objective**

To develop a model to determine whether a single dose steroid challenge can be used to predict GC responsiveness in subjects with HES

### **2.2. Secondary Objectives**

To define a group of GC non-responders and/or suboptimal responders for further study of the mechanisms and biologic correlates of GC resistance in HES

### **2.3. Exploratory Objectives**

To delineate some of the mechanisms of decreased GC responsiveness in GC-resistant subjects and to assess in-vitro correlates of therapeutic responsiveness in HES in a subset of subjects.

## **3. Study Design and Methods**

### **3.1. Description of the Study Design**

The study is designed as a single center, open label, single-blinded observational study to develop a model to assess whether a single dose steroid challenge can predict GC responsiveness in subjects with HES. GC responsiveness is defined as the minimum dose of GC required to control eosinophilia and symptoms.

### **3.2. Screening**

Subjects with HES enrolled on Protocol #94-I-0079 (Eosinophil Characterization, Activation, and Function in Parasitic Infections and other Conditions with Increased Tissue or Peripheral Blood Eosinophilia in Humans) will be recruited for enrollment in this protocol. Since eligibility for this protocol will be determined on the basis of the standard clinical and laboratory evaluations performed as part of Protocol #94-I-0079, a separate screening visit will not be necessary for the GC challenge. Since the HES workup may need to take place over several visits, to determine eligibility, a CBC with differential will be performed at the NIH or at the patient's local site within 14 days prior to enrolling on this protocol.

Informed consent will be obtained and subjects will be enrolled during a scheduled visit for protocol 94-I-0079 or via telephone prior to undergoing any procedures specific to this protocol. Telephone consents will be obtained according to current NIH policy (section 7.5.3).

### 3.3. Baseline Visit

Baseline assessments and procedures will be performed up to 90 days prior to dosing with prednisone and will include (see Appendix B for complete list):

- A complete history and physical examination, with emphasis on signs and symptoms associated with eosinophilia (i.e. fatigue, pruritus, skin involvement, neuropathy, arthralgias, myalgias etc.)
- Routine laboratory studies, including complete blood count with differential, routine chemistries including electrolytes, liver and kidney panels.
- Additional diagnostic testing, as clinically indicated, to characterize baseline clinical manifestations of eosinophilia.
- Blood  $\beta$ -HCG at baseline visit. Urine  $\beta$ -HCG will be performed in the morning prior to prednisone administration in women of childbearing potential.
- Assessment of eosinophil activation, additional research studies and storage of samples as outlined in Appendix C.

### 3.4. Procedures and Laboratory Testing

Subjects will receive a single dose of prednisone prescribed by the PI or designee to be taken by mouth at a dose of 1 mg/kg (rounded to the nearest 5 mg) between the hours of 7:30 and 9am on the day of study. Laboratory testing, including a baseline cortisol level, CBC with differential, and research specimens (see Appendix B) will be drawn prior to prednisone administration and at 2, 4 and 24 hours after prednisone administration. Investigators will be blinded to the 2-hour, 4-hour and 24-hour eosinophil counts (the results will not appear in the NIH Clinical Research Information System (CRIS), but will be available from the Clinical Pathology internal system for analysis once the trial is completed). All blood draws will be timed and will occur in outpatient phlebotomy, outpatient clinic or inpatient unit that is able to draw at specific times to prevent variability in draw times across the subject cohorts.

In normal subjects, prednisone is rapidly absorbed and metabolized with peak levels at 2-4 hours and a biologic half-life of 12-36 hours. Serum will be stored from blood drawn at the 4-hour time point for assessment of synthetic glucocorticoid levels, including prednisone and its metabolite prednisolone. Subjects may be asked to undergo further workup for causes of poor absorption by their home physician or at NIH if indicated.

After the 24-hour challenge, subjects will be started on a GC taper to determine the lowest dose of GC that is able to suppress signs and symptoms of HES and maintain the peripheral eosinophil count below 1000/ $\mu$ l. GC will be initiated at 30 mg in all subjects, and the taper will proceed according to an algorithm (Appendix E). GC will be tapered by 5 mg weekly until a dose of 15 mg is reached. The dose will then be tapered by 2.5 mg weekly until a dose of 5 mg is reached or the eosinophil count rises.

In some cases, an initial starting dose of 30 mg of prednisone will be insufficient to control eosinophilia. If AEC is  $>1000/\mu$ L 1 week after the initiation of GC, the GC dose will be increased to 60 mg and a taper initiated from this higher dose. A CBC with

differential will be drawn after 2 days on this higher dose and if the AEC remains  $>1000/\mu\text{L}$ , the subject will be withdrawn and total GC dose used for the final analysis will be the weight-based challenge dose for that individual. If the subject is responsive at the higher dose, the subject will be kept at 60 mg for one week after which the GC dose will be tapered by 10 mg every week until a dose of 30 mg of prednisone is reached. If AEC is still suppressed and they are able to continue the taper, they will then taper according to the standard taper schedule outlined above and shown in Appendix E.

Weekly eosinophil counts will be obtained with the taper until the AEC rises above  $1000/\mu\text{L}$  or the subject experiences HES symptoms. HES symptoms will be defined by the investigator and will be based on data collected at the time of the baseline visit, as well as clinical experience in the treatment of HES. If either eosinophils rise or HES symptoms are present, prednisone will be increased to the previous dose, and a taper will be re-attempted. If the AEC increases after an attempted decrease in dose, the rate of the tapering schedule will be decreased to 2.5 mg/week from 5 mg/week. The taper will continue according to this schedule until 2 attempts to taper from a given dose fail or a dose of 5 mg of prednisone is reached. If a subject's AEC continues to climb despite a dose increase, at the discretion of the investigator the dose may be increased by a larger dose than outlined in Appendix E. Attempts to capture the true effective dose of glucocorticoid that controls counts and symptoms will be attempted; however if not practical due to time or side effect profile of prednisone, subjects will return for an end of study visit and be removed from the study. If a subject is unable to be tapered, their responsiveness, or lack thereof, will be captured at that dose. Depending on the dose and the clinical presentation they may be continued on prednisone however they will be withdrawn from the protocol at the dose at which they were no longer able to taper.

The GC taper will be individualized in subjects in whom a prolonged course of a higher dose is clinically indicated (e.g., Churg Strauss syndrome/EGPA) or a slower taper is needed to prevent steroid withdrawal. Investigators will not be blinded to the eosinophil counts obtained during the taper, as the primary endpoint is dependent on the initial results of the steroid challenge to which the investigators are blinded.

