### **3.5. Study Endpoints**

#### **3.5.1. Primary Endpoint**

The primary response variable is GC responsiveness, defined as the lowest dose of prednisone at which eosinophils remain  $<1000/\mu\text{l}$ , for at least two consecutive weekly blood draws, and at which symptoms are controlled as determined by the investigator; OR, dose of prednisone at which subject is unable to taper prednisone further without rebound of eosinophilia and/or symptoms after three attempts; OR, the challenge dose, if there is no drop in eosinophil counts within the first week of challenge or taper.

GC responsiveness in each individual will be assessed using the percent change in eosinophil count (eosinophil response rate [ERR]) from baseline to 4h (or 24h) post-steroid challenge.

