## 6.3. Final Analysis Plan

### 1. Study Endpoints:

- Primary: GC responsiveness.
  - Definition: See primary endpoint for definition of GC responsiveness.
  - Validity and Reliability: This is a rare disease, and standard care for this disease is still being developed. There is no standard endpoint, and this endpoint has not been used before. One of the purposes of this study is to see if this endpoint can be reliably predicted. The endpoint has face validity because the dose that controls eosinophil concentration is useful for determining the extent of a subject's disease and their responsiveness to steroid therapy. We will first try and predict GC responsiveness as described in section "Description of the Analyses" (Section 6.1), but may also try to predict the categorization of the GC responsiveness into 3 ordered categories described in section "Description of the Analyses".
  - Predictor Variables: All predictor variables will be measured in the first 24 hours after initial dose, and will be blinded to the PI and Accountable Physician. These variables will be used to predict the GC responsiveness:

percent change in eosinophil count from baseline to 4 and 24 hours and steroid absorption.

- Secondary:
    - Classification of subjects by GC response for assessment of clinical factors associated with GC responsiveness (including HES variant, pattern of organ involvement and laboratory parameters)
  - Exploratory
    - Exploratory analyses of potential mechanisms and in vitro correlates of GC resistance, including impaired steroid absorption, cell surface markers on lymphocytes, intracellular and serum cytokine profiles.
2. Description of the Statistical Methods to Be Employed:
    - Spearman correlation of GC responsiveness and percent change in eosinophil from baseline to 4 and 24 hours, with confidence intervals and testing whether it is different from zero.
    - Model building as described in section “Description of the Analyses” (Section 6.1).
  3. Level of Significance to be Used: Two-sided 0.05
  4. Exploratory Analyses: See section 6.1 for primary objective. Similar model building strategies will be used for secondary endpoints and exploratory endpoints.

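### Subjects who fail 60 mg are scored by body weight, sections 3.4 and 3.5.1 disagree on who gets that score, and the scheduled 15 mg step belongs to no response category

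*Combined protocol and SAP*

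**What the plan says.** The primary outcome is a dose. Section 3.1 states that "GC responsiveness is defined as the minimum dose of GC required to control eosinophilia and symptoms", so a lower value means a better response. Several places say how the value is assigned.

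- **Section 3.4, 60 mg step.** A subject with a count above 1000/µL after a week on 30 mg goes to 60 mg. If the count is still above 1000/µL two days later, the subject is withdrawn and the "total GC dose used for the final analysis will be the weight-based challenge dose for that individual". The same section sets the challenge dose at 1 mg/kg, rounded to 5 mg.
- **Section 3.4, end of taper.** "If a subject is unable to be tapered, their responsiveness, or lack thereof, will be captured at that dose". A subject controlled on 60 mg who cannot go lower therefore scores 60. Tapering ends at 5 mg or after two failed attempts from one dose.
- **Section 3.5.1.** Three alternatives are joined by OR, with no order of precedence. The first is the lowest dose with counts under 1000/µL at two successive weekly draws and symptoms controlled. The second is the dose at which the subject is "unable to taper prednisone further without rebound of eosinophilia and/or symptoms after three attempts". The third is "the challenge dose, if there is no drop in eosinophil counts within the first week of challenge or taper".
- **Section 5.6, item 3.** Complete non-response is described as no reduction from baseline on 30 mg or on 60 mg. Such subjects stay in the analysis, but no value is given for them.

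For the primary endpoint, section 6.3 says only "See primary endpoint for definition of GC responsiveness", and section 6.4 also points to 3.5.1. The missing-data item in 6.3 says that subjects not controlled on 30–60 mg nevertheless have an endpoint. Section 6.1 sets three categories (below 15 mg, 16 to 40 mg, above 41 mg), and section 3.5.2 uses them for the secondary endpoint.

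**The concern.** One scale carries two different quantities. For controlled subjects it is the dose that worked. For 60 mg failures it is body weight in another form. The failures are the group that the secondary objective sets out to identify, and their order on the primary outcome, both among themselves and against subjects controlled at high doses, depends on weight. The score enters the Spearman test as a rank and the linear models as a number, where the spacing matters as well.

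In addition, two analysts following different sections could give the same subject different values, or one of them no value. A subject who ends at 15 mg could not be classified for the secondary endpoint or in the fallback cumulative logit model.

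**Working it through.** **1. The plan's own figure.** Section 6.2 states 79.5% power for Spearman at n = 32, correlation 0.5, two-sided 0.05. A simulation of 60,000 bivariate normal data sets gives 79.95%, so the figure reproduces. For Pearson, ((1.960 + 0.842)/atanh 0.5)² + 3 = 29.01, against a stated 29. The sample size calculation is not in dispute.

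**2. Score of a 60 mg failure.** Score = 5 × round(weight in kg / 5).

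| Weight (kg) | Score (mg) | Against a subject controlled only at 60 mg |
|---|---|---|
| 48 | 50 | ranks as more responsive |
| 57.4 | 55 | ranks as more responsive |
| 57.6 to 62.4 | 60 | tied |
| 62.6 | 65 | ranks as less responsive |
| 100 | 100 | ranks as less responsive |

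The inversion can occur: section 4.2 admits minors from 48 kg and sets no weight floor for adults.

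**3. Share of failures affected.** The documents give no weight distribution, so normal weights are assumed. P(score < 60) = Φ((57.5 − μ)/σ). P(tie) = Φ((62.5 − μ)/σ) − Φ((57.5 − μ)/σ).

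| Mean/SD (kg) | Below 60 mg | Tied at 60 mg |
|---|---|---|
| 70/15 | 20.2% | 10.6% |
| 70/18 | 24.4% | 9.5% |
| 75/16 | 13.7% | 8.0% |
| 80/15 | 6.7% | 5.5% |
| 80/18 | 10.6% | 6.0% |

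At 75/16, the 5th and 95th weight percentiles are 75 ± 1.645 × 16 = 48.7 and 101.3 kg. Failures alike in response would thus score from 50 to 100 mg.

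**4. Who receives the challenge-dose score.**

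| Subject | Section 3.4 | Section 3.5.1 |
|---|---|---|
| 10,000/µL at baseline, 3,000 after week 1 on 30 mg, 1,200 after two days on 60 mg | challenge dose | no alternative met: never under 1000, no taper attempted, and a 70% drop in week 1 |
| No drop in week 1, then controlled on 60 mg | taper-derived dose | meets the challenge-dose alternative, and can also meet the first |
| No drop in week 1, then fails 60 mg | challenge dose | challenge dose |

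Of these three patterns, the sections agree only on the last. They also differ on failed tapers: two attempts in 3.4, three in 3.5.1. Section 5.6 adds a third description of non-response.

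**5. Categories.** The taper described in 3.4, including the slowed 2.5 mg rate, can reach 60, 50, 40, 30, 27.5, 25, 22.5, 20, 17.5, 15, 12.5, 10, 7.5 and 5 mg. Of these 14 doses only 15 mg has no category. Weight alters a failure's category only below 42.5 kg, where the score is 40 mg or less and falls in moderately responsive. Minors that light are excluded, so this concerns adults only.

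**6. Effect on the Spearman test.** The simulation (10,000 replicates) took n = 32, latent correlation 0.5, weights 75/16, and the least responsive fraction as failures. An inversion is a failure scored strictly below a controlled subject. The even spread places controlled subjects equally over 11 doses (5, 7.5, 10, 12.5, 15, 20, 25, 30, 40, 50 and 60 mg). The sparse spread puts 1% at each of 40, 50 and 60 mg.

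| Failures | Controlled doses | At least one inversion | Power as written vs tied worst rank |
|---|---|---|---|
| 15% | even | 46.8% | 79.0% vs 80.0% |
| 15% | sparse | 14.4% | 79.1% vs 79.1% |
| 30% | even | 68.4% | 74.6% vs 77.3% |
| 30% | sparse | 20.3% | 75.5% vs 77.4% |

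At 15% failures the mean number of inverted pairs is 2.07 (even) or 0.23 (sparse), out of 32 × 31/2 = 496. Repeat runs of the 15% rows gave 46–47% and 15%. In a separate run with lighter subjects (65/13, even spread), the power loss was 79.6 − 77.9 = 1.7 points at 15% and 77.8 − 73.9 = 3.9 points at 30%.

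**The case against.** The best defence is that section 3.4 says expressly what the final analysis uses for a 60 mg failure, and the missing-data item in 6.3 confirms that such subjects have an endpoint. Read together, the specific rule supplies the value and 3.5.1 merely fails to repeat it. This stands in part: a reader might infer that the partial responder in step 4 drops out of the analysis, but 3.4 does give that subject a value. It does not settle the subject with no first-week drop who is then controlled on 60 mg, because there 3.5.1 actively assigns a different value.

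The effect on the test is small, section 6.1 calls the primary objective exploratory, and the higher inversion chances need 3/11 = 27% of controlled subjects to end at 40–60 mg, which nothing in the documents supports. All of that stands.

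The resistant category already covers subjects with or without a response. That stands too: a reader might infer that weight distorts the three-category endpoint broadly, but only adults under 42.5 kg are affected, about 0.6–6.3% of failures under the weights in step 3.

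A reader might also infer that controlled subjects can end above 60 mg, which would widen the inversion, since 3.4 says that "the dose may be increased by a larger dose than outlined in Appendix E". The documents do not say that such an increase passes 60 mg, so no figure rests on it.

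Finally, recoding now is a late change, after about two thirds of projected subjects have completed and with taper counts unblinded. Keeping the written score as primary with a ranked sensitivity analysis would be defensible. This is why both codings should be reported; it does not remove the need to reconcile the sections.

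**Conclusion.** The point holds on the text alone in three respects. The failure score follows body weight, with inversion below 57.5 kg and ties from 57.5 to under 62.5 kg. Sections 3.4 and 3.5.1 assign that score on different tests and count failed tapers differently. The scheduled 15 mg step has no category.

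The size is illustrative, because the documents give no distribution of weight, non-response or end dose. The retrospective response rate above 85% at one month (section 1.1) is only a loose guide to the 15% used. Under the stated assumptions, 6.7–24.4% of failures score below 60 mg. At n = 32, weights 75/16 and 15% failures, the chance of any inversion is about 15–47%, and the power loss is about 0–1 point (about 2–3 points at 30% failures). A reader might conclude that the trial is underpowered or the sample size wrong; the figures do not support that. What is at fault is the validity and completeness of the endpoint. Appendix E, a figure not available in the text, was not relied on.

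**What to change.** (a) Reconcile sections 3.4, 3.5.1 and 5.6, including two versus three attempts, into one analysis definition that gives every subject exactly one value. Its content is for the sponsor to decide.

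(b) In the Spearman test, give all subjects who meet the reconciled non-response definition a common tied worst rank, and class them as resistant whatever their weight.

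(c) In the linear models, use one pre-specified analysis code (a score, not a dose) above the highest end dose of any controlled subject, or an ordinal or censored treatment. Add a sensitivity analysis over other codes.

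(d) Report the weight-based scoring of section 3.4 alongside. Validate any interim model already fitted on the coding used to fit it. Record the date of the change and what was unblinded by then.

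(e) Make the three categories exhaustive; the sponsor chooses the side on which 15 mg falls.

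The recoding needs no new data. The cost is a documented late change in outcome coding, loss of gradation among non-responders (partial and absent responders merge if the definition covers both), and two codings to report.
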